Patients on peritoneal dialysis have frequent complications requiring hospitalization. Overhydration (OH), a qualitative description of fluid status, with excess fluid in the extracellular space [9], is one of the most common complications in PD patients. Clinical manifestations of OH include peripheral edema, congestive heart failure, pleural effusions, and hypertension [9]. It is estimated that 50-60% of PD patients are overhydrated, with severe OH producing clinical symptoms in 25% [10,11]. OH is associated with increased morbidity and mortality due to infections including peritonitis [12], and major adverse cardiovascular events such as myocardial infarction, pulmonary edema, stroke, and hypertensive crisis [9]. OH alone, independent of coexisting cardiovascular pathologies, is a risk for increased morbidity and mortality [13]. In 2016, at Srinagarind Hospital, at Khon Kaen University (KKU), Thailand, nearly half of the PD patients were hospitalized at least once, and some were hospitalized 2-4 times. Thirty-nine of the 91 patients (43%) were hospitalized a total of 77 times (some had 2-4 admissions). Sixty-five percent (50/77) of the hospitalizations were OH related (Table 1). The 5-year survival rate for PD patients is 48% [14]. Sixty-five percent of the PD admissions were for OH and related complications, with an average cost of \$3,000 USD/admission [14]. Extrapolating this data to a national level, the estimated cost for OH-related admissions in PD patients in Thailand is \$37,500,000 USD/year.

CKD and mobile health technology

Early treatment of overhydration can decrease complications and hospitalizations, improve quality of life, and decrease costs for PD patients. OH can be managed with treatments such as diuretics and anti-hypertensive medications, adjustments in dialysis prescriptions, and sodium/fluid restrictions [9,15]. Early detection of OH is possible by monitoring patients' hydration metrics: weight, blood pressure (BP), and ultrafiltration volume (difference between fluid input and output in dialysis). Currently, the critical gap lies in obtaining these hydration metrics in a timely and actionable format. A few studies have shown that smartphone and tele-monitoring programs are feasible and acceptable for patients with CKD [16-19]. Remote monitoring systems for PD patients

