Inclusion of children: We will enroll patients 18 years of age or older. The prevalence of PD in patients in Thailand under 18 years of age is <1% [8], therefore making it difficult to include this age group in our study. In addition, the etiologies of chronic kidney disease and co-morbidities are different in children and PD is used less frequently in children compared to hemodialysis.

Collaborating sites: None

Statistical Design and Power: We determined our sample size by using the difference in incidence rates between two Poisson means with 25% precision. Data collected from Srinagarind Hospital indicate the intervention rate for OH, based on current practice of patients contacting the PD clinic staff with symptoms or concerns of OH outside of scheduled appointments, to be 4 times/week in 91 patients or a mean intervention rate of 2.3 times/patient-year. Assuming a two-fold increase in the mean event rate for patients using the CKD-PD app or

4.6 times/patient-year in the CKD-PD app group, the desired sample size is 80 patients for each group, using a two-sided, large-samples z-test of the Poisson event-rate difference at a significance level of 0.05. Allowing for a 10% dropout rate, we will recruit a total of 200 patients (100 in each group). Our assumption that use of CKD-PD app will result in a twofold increase in the incidence of clinical interventions is based on our preliminary experience with the 42 patients currently using the CKD-PD app. In those 42 patients, especially those with unstable fluid and blood pressure control, the app frequently identifies outlier measurements resulting in intervention opportunities which are not possible in the no-app control group.

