Baseline variables of the CKD-PD app and no-app groups will be described by summary statistics. Percent distribution will be presented for all categorical variables. Mean with its standard deviation and median (Minimum: Maximum) will be presented for continuous variables. The primary outcome will be assessed by comparing the difference between the CKD-PD app group (intervention) and the no-app group (control), in incident rate (or Poisson count) of intervention for OH. A linear mixed model with an identity link and a Poisson distribution will be performed. By this modeling, the incidence rate difference and its 95% confidence interval will be estimated to answer the primary research question. Estimations will be adjusted for effects of important covariates that are imbalanced at baseline. Effect size will be calculated for secondary outcomes. All analyses will be performed using STATA version 14 (StataCorp, College Station, TX), using a significance level of 0.05. All statistical tests will be two-sided.

Randomization

Participants (Srinagarind N=100, Khon Kaen N=50, Chaiyaphum N=50) will be randomized into two equal groups at each site, one using the CKD-PD app (app group, N=50/25/25), and one receiving usual management (no-app group, N=50/25/25), using 4-block computer randomization in STATA. They will be assigned a PD clinic visit day based on their randomization allocation to reduce contamination or cross talk between the 2 study groups.

Delivery of intervention

Definition of study intervention:

Our study intervention is defined as the CKD-PD app, home hydration metric measurement equipment, and the monitoring of the uploaded hydration metrics to the CKDNET database.

Collection of hydration metrics: After enrollment, participants in both groups will undergo training on how to collect daily hydration metrics: body weight, blood pressure, and dialysate inflow and outflow volumes for each cycle. The app group will receive training on how to enter hydration metrics using NFC on the CKD-PD app, in

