2. *Clinical intervention for overhydration:* Change in medical treatment in response to OH detected by clinical symptoms or hydration metrics. Interventions may include a change in medications to treat OH such as anti-hypertensives or diuretics, dialysis prescription, dietary sodium/fluid restriction, referral for evaluation in clinic, or hospitalization. This information will be collected in the electronic PD clinic study log at the time of the clinical intervention.
3. *Unscheduled clinic contacts:* When patients in either group make an unscheduled contact with the PD clinic this will be recorded in the PD clinic electronic study log. Unscheduled clinic contact can also occur in the “app” group when PD clinic staff contact a patient in response to abnormal hydration metrics. Unscheduled contacts include any phone call, text, social media, or web app message, and unscheduled visit to the PD clinic or emergency department. The information collected included patient name/MR#, reason for contact, mode of contact, who initiated contact, date and time of day, and action taken. Unscheduled clinical interventions will be recorded at the time of the event.
4. *Scheduled clinic contacts:* Patients in both groups will have regularly scheduled clinic visits, typically bimonthly. Clinical interventions for OH made during this visit will be recorded in the electronic PD clinic study log. A medical record review will also occur at each visit to collect any other hospitalizations, complications, or clinical interventions that may have occurred in the interim.
5. *CKDNET database review:* In order to ensure all events have been captured, we will review the CKDNET database, which has all inpatient and outpatient visits, on a bimonthly basis.

Data collection overview

Data elements for analysis of covariates at enrollment: These will include: age, sex, educational level, cause of CKD, eGFR, co-morbidities (e.g. diabetes, hypertension, albumin level), previous hospitalizations for OH, smoking status, distance from clinic, months on PD, months of CKD-PD usage, and app user type (patient or surrogate). The source will be medical records and patient interview at time of enrollment.

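### Primary adjustment depends on observed baseline imbalance and leaves out site, at a modest cost in precision; the mixed model's random effect also needs naming

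*Combined protocol and SAP*

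**What the plan says.** The primary analysis is described only under Aim 2, Statistical Design and Power. The model is given as "A linear mixed model with an identity link and a Poisson distribution will be performed", from which the incidence rate difference and its 95% confidence interval are to be estimated. The covariate rule is "Estimations will be adjusted for effects of important covariates that are imbalanced at baseline". A covariate must meet both conditions to enter the model. Neither condition is defined, and the only baseline comparison planned is descriptive: "Baseline variables of the CKD-PD app and no-app groups will be described by summary statistics".

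The Data collection overview lists candidates under "Data elements for analysis of covariates at enrollment", among them previous hospitalizations for overhydration and diabetes. It commits none of them to the model. The list ends with "months of CKD-PD usage, and app user type (patient or surrogate"), and it does not include site.

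The Randomization section says that participants "will be randomized into two equal groups at each site", 50/25/25 per arm, in blocks of four. No section gives site a role in the analysis. The model is called mixed, but no random effect, grouping level or variance estimator is named.

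**The concern.** Under randomization, baseline imbalance is chance. It says nothing about whether a covariate predicts the outcome. Adjustment gains precision from prognostic strength, whether or not the covariate happens to balance, so the rule selects on the wrong property. It also cannot be carried out as written: with no test or threshold, the analyst decides what counts as imbalanced after seeing the baseline data.

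Precision is the plan's own standard, because the sample size rests on the "difference in incidence rates between two Poisson means with 25% precision". Site is the randomization stratum, so a variance estimate that ignores it can overstate the uncertainty.

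A separate question is whether the model captures differences between patients in their underlying intervention rate. If it does not, the primary confidence interval would be too narrow.

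**Working it through.** **1. The plan's sample size.** Inputs (Statistical Design and Power): rates 2.3 and 4.6 per patient-year, difference 2.3, precision 25%, two-sided 0.05, one year of follow-up. n per group = 1.96² × (2.3 + 4.6) / (0.25 × 2.3)² = 80.2. The stated 80 reproduces as a confidence-interval-width figure with no covariate, site term or random effect.

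**2. Power at the planned effect.** SE = √(6.9/80) = 0.294 and 2.3/0.294 = 7.8 SEs. With an SE 11% larger, 7.8/1.11 is about 7. On the plan's own Poisson figures the rule does not put power at risk.

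**3. Precision lost by the rule.** Take one covariate with covariate-outcome correlation r (assumed). Relative to always adjusting, the variance ratio is [(1 − r²) + r²m] / (1 − r²). Here m = E[z²; not flagged] is the part of the chance imbalance that stays unadjusted. For a 5% test, m = 0.72. The SD ratios for 80 to 100 per arm are:

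| Imbalance trigger (assumed) | r = 0.2 | r = 0.3 | r = 0.5 |
|---|---|---|---|
| 5% test | 1.015 | 1.035 | 1.11 |
| 10% test | 1.01 | 1.03 | 1.09 |
| Standardized difference > 0.2 | 1.01 | 1.02 | 1.06-1.07 |
| Standardized difference > 0.1 | 1.001-1.002 | 1.003-1.004 | 1.010-1.013 |

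Simulated trials (20,000 per setting) agree, with type I error under the rule between 3.8% and 5.2%. A separate gamma-Poisson simulation under no effect (dispersion 0.5, binary covariate with 40% prevalence) gave empirical SEs with a 5% trigger of 0.386 against 0.368 when always adjusting, at rate ratio 2. At rate ratio 3 they were 0.399 against 0.361. The ratios are 1.05 and 1.11, with no material bias.

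**4. What those correlations require.** For a binary covariate with prevalence 0.4, rate ratio R, arm mean μ and residual dispersion 0.5 (assumed), let b = μ/(0.6 + 0.4R). Between-level variance is B = 0.24 b²(R − 1)². Within-level variance is W = μ + 0.5(0.6b² + 0.4R²b²). Then r = √[B/(B + W)]. Over the two arm means, R = 1.35 gives r of 0.15-0.17, R = 1.8 gives 0.29-0.32, and R = 3 gives 0.46-0.50. The 11% loss therefore needs one covariate that roughly triples the rate, together with a strict 5% trigger.

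**5. Site.** With 1:1 allocation within site, omitting site loses no true precision. If two sites' rates differ from the largest site's by ±d (assumed), a robust SE that ignores site is too wide by √{1 + 26.45(d²/2) / [6.9 + 26.45k(1 + d²/2)]}. Here 26.45 = 2.3² + 4.6² and k is the dispersion (0.27 or 1.33, assumed). The result is 1.01-1.04 at d = 0.3 and 1.035-1.105 at d = 0.5.

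**6. The random effect.** With rate 2.3 in both arms and variance μ + kμ², a plain Poisson SE gives type I error 2P(Z > 1.96/√(1 + 2.3k)). This is 12%, 18% and 28% at assumed k = 0.25, 0.5 and 1.0.

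The only clustering data in the protocol concern admissions (Peritoneal dialysis and overhydration): "Thirty-nine of the 91 patients (43%) were hospitalized a total of 77 times", some with 2-4 admissions. If 4 is the maximum per patient, the extreme distributions are:
- 77 admissions, least spread (1 patient with 1, 38 with 2): mean 0.846, variance 153/91 − 0.846² = 0.965, k = (0.965 − 0.846)/0.846² = 0.17.
- 77 admissions, most spread (26 with 1, one with 3, 12 with 4): variance 227/91 − 0.846² = 1.779, k = 1.30.
- 64 admissions, the sum of the Table 1 rows and the base that fits its percentages (21/64 = 33%): k = 0.11 (14 with 1, 25 with 2) to 1.18 (30 with 1, one with 2, 8 with 4).

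For k of 0.11 to 1.30 the type I formula gives about 8% to 33%, if interventions cluster like admissions (assumption).

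**The case against.** The strongest reply is that the effect is small and that the plan is not unprincipled. Candidate covariates are listed in advance, the rule restricts them to important ones, and choosing among them needs no outcome data. At a covariate rate ratio of 1.35 the loss is at most about 1.5% under any of the triggers above. All of that stands, and it keeps this point a modest efficiency improvement.

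Four stronger readings are tempting, and the documents do not support them.

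- A reader might infer that the rule biases the result or inflates type I error. It does neither.
- A reader might take 11% as the expected loss, or add it to the planned 25% precision. The 11% needs a very strong covariate and a strict trigger that the plan does not state. The 25% itself holds only without overdispersion: at k = 0.25 to 1.0 the half-width is 1.96 × √[(6.9 + 26.45k)/80] / 2.3, or about 35% to 55%.
- A reader might infer that the primary interval will be too narrow. That follows only if the random effect is not at patient level and the SE is also plain Poisson. The plan says mixed, which may well mean a patient-level effect. With three sites, a site-level effect is also a natural reading and would not capture patient differences.
- A reader might take the admissions data as showing how interventions are dispersed. Admissions are a different event, and interventions include medication and diet changes.

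A further objection is that adding covariates strains the identity link. That is correct, and the fix has to provide for it.

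**Conclusion.** The point holds as a worthwhile improvement at low cost. Tying adjustment to observed imbalance, and giving the randomization stratum no analytic role, gives up precision for no benefit. The likely loss runs from negligible to a few percent of the SD. It approaches 11% only at the edge of the assumptions, and it depends on a trigger and covariate strengths that the plan does not give. Leaving out site affects the stated SE and not the true precision.

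The unnamed random effect is a secondary request for clarification. It matters to error control only under the two conditions given above, and the dispersion of intervention counts is unknown. If both conditions applied, the consequence (type I error of 12-28% at assumed dispersion 0.25-1.0) would be larger than anything the covariate rule does, so it deserves an explicit sentence.

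**What to change.** Replace the adjustment sentence with: *The primary model will include site (three levels) and a short list of prognostic baseline covariates fixed before outcome data are reviewed (for example previous OH hospitalization and diabetes), irrespective of observed balance; imbalance-driven adjustment is a sensitivity analysis.*

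State either a patient-level random effect or a robust (overdispersion-adjusted) SE.

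Add: *If the identity-link model does not converge or gives a fitted rate at or below zero, the rate difference will be obtained by standardization from a log-link model with the same covariates and a robust SE.*

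Use duration of app use and type of app user only as values recorded before randomization in both arms. Otherwise they may be undefined or zero in the no-app group.

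Cost: wording only. The example covariates are already collected at enrollment and the sample size is unchanged. The model uses about four degrees of freedom (two for site, two for covariates) in 160-200 patients. The real downside is fitting. In simulated trials with site and two binary covariates (80 per arm, assumed effects), the identity-link model had no valid solution in 0-13% of runs. The log-link fallback fitted in every run and was close to unbiased (mean difference 2.29-2.32 for a true 2.3), with type I error 4.8-6.2%. Keeping the list to binary or few-level covariates limits how often the fallback is needed.

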the same hydration metrics - blood pressure (BP), weight, and ultrafiltrate volumes - using home monitoring equipment (BP cuff, body weight scale, and hanging scale). The no-app group will manually enter the information into their “PD logbook”- the handwritten paper booklet which is usual care. In contrast, the app group will automatically collect and enter the same information into the CKD-PD app using NFC technology on their smart phone. It will be displayed in the CKD-PD app for the patient and uploaded to the CKDNET database in the Thai Care Cloud; it then can be viewed on the CKD-PD web application by the PD clinic staff. Patients will monitor their hydration status on a graphical display on their smartphone. PD clinic staff will be notified daily about “action required” alerts on the web application. For example, systolic BP greater than 140 mmHg, diastolic BP greater than 90 mmHg, weight gain greater than 3% based on dry weight, or ultrafiltrate volume < 500 milliliters will trigger a response from the PD clinic. Nephrologists will make clinical interventions to treat OH according to standard practice in Thailand, which include BP and diuretic medication adjustments, change in diet or fluid intake, dialysis prescription adjustments or referral for urgent clinical evaluation. Clinical interventions can occur at unscheduled patient contact (e.g. patient call) or scheduled patient contact (routine clinic visit) Our primary outcome measure will be the incidence of clinical interventions for OH, both routine and urgent, in 1 year from enrollment. Secondary outcome measures include OH related complications, hospitalizations and deaths, and will be collected from PD clinic and hospital records, and the CKDNET database.

Setting and study population: The study will be conducted at the PD clinics at Srinagarind Hospital (N=100) the academic referral hospital affiliated with Khon Kaen University, Khon Kaen Hospital (N=50) the government referral hospital for Khon Kaen province, and Chaiyaphum Hospital (N=50), the government referral hospital for the neighboring Chaiyaphum province in northeast Thailand. We will recruit 200 patients with end-stage renal disease on PD from KKH to achieve a total sample size of 160.

Inclusion criteria are

- patients with CKD from any cause on home based peritoneal dialysis
- age ≥ 18
- access to a smartphone capable of running the CKD-PD app
- ability of the patient or surrogate to demonstrate successful use of the CKD-PD app

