
Exclusion criteria are

- vulnerable populations
- unwillingness to sign consent or participate in the study.

Recruitment plan: The study population will be recruited from patients at the nephrology clinic at each of the participating hospitals who are undergoing peritoneal dialysis. Participants will be recruited over a 3-month period

at scheduled PD clinic appointments. This is feasible since all patients are seen within a 2-month interval. Accrual will be monitored by Thai study staff by recording enrolled participants in the electronic study log and a list of patients from KKH who declined enrollment or were excluded. Participants will be informed about the possibility of participating in a research study using a smartphone app to help collect information about the peritoneal dialysis, which they currently collect using a handwritten log book. They will be provided with written and verbal information about the research. All questions will be answered. Participation is completely voluntary, and participants can withdraw from the study at will.

Retention plan: Retention will be maximized by frequent involvement and contact with the research team and PD clinic staff. Patients undergoing peritoneal dialysis already require frequent clinic contact and they have a long-standing relationship with the MDs and RNs in the nephrology clinic. Compliance with PD clinic appointments is estimated at over 90%; participants who miss their scheduled appointments will be contacted by PD clinic and rescheduled.

Planned distribution of subjects by sex/gender, race, and ethnicity: We will not select or reject patients based on gender, race or ethnicity. The racial and ethnic composition of the general population, the PD patient population, and the research study population is nearly exclusively Thai. The study will take in place at Khon Kaen province, located in an area of nearly exclusively Thai ethnicity. We expect nearly equal numbers of male and female enrollment given the nearly equal rates of PD between the sexes. We base this assumption on the reported prevalence of females on PD (50.8%) and males (49.2%) [8].

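### Fixed blocks of four within each site, with the block size printed in the protocol and arms visible once assigned, could make up to about one third of allocations knowable in advance

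*Combined protocol and SAP*

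**What the plan says.** The allocation procedure is in Aim 2, Randomization. "Participants (Srinagarind N=100, Khon Kaen N=50, Chaiyaphum N=50) will be randomized into two equal groups at each site", with the "app group, N=50/25/25" and the no-app group of the same sizes, "using 4-block computer randomization in STATA". The same paragraph adds: "They will be assigned a PD clinic visit day based on their randomization allocation". No variation in block size, holder of the list, method of concealment or moment of release is described.

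The arms differ visibly. In the Aim 2 overview, "the app group will automatically collect and enter the same information into the CKD-PD app using NFC technology on their smart phone", while the other arm keeps a paper logbook. App-group patients also receive a home visit at the start of data collection.

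On enrolment, the Aim 2 recruitment plan says "Participants will be recruited over a 3-month period", at routine PD appointments, with all patients seen within two months. "Accrual will be monitored by Thai study staff by recording enrolled participants in the electronic study log". The Aim 2 inclusion criteria require "ability of the patient or surrogate to demonstrate successful use of the CKD-PD app". They do not say who judges this, when, or against what standard.

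**The concern.** With a fixed and known block size, prediction does not require sight of the list. The assignments already made in the current block are enough, and here those show in the equipment and the clinic day. Hiding the list would therefore not remove the problem by itself.

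Foreknowledge matters only if enrolment can respond to it. Two features leave some room: an eligibility check with no written standard, and enrolment at routine visits, where a patient can be taken now or at a later visit.

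The direction of a possible bias is plain. Under Statistical Design and Power, the expected doubling of the intervention rate is justified by experience with 42 app users, particularly those whose fluid and blood pressure were unstable. If such patients entered the app arm preferentially, the primary count would rise there whether or not the app did anything. Adjustment for measured baseline imbalance would not reach a clinician's unrecorded impression of the patient.

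**Working it through.** The plan states no figure for predictability, so there is none to reproduce. The inputs are the block scheme, the 1:1 ratio and the site sizes of 100, 50 and 50, all from Aim 2, Randomization.

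1. **Meaning of the block description.** Four blocks per site would give blocks of 100/4 = 25 or 50/4 = 12.5, and neither splits 1:1. Block size four is the workable reading.

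2. **Certain allocations in one block.** There are six equally likely orders of two A and two B. Places 1 and 2 are never determined. Place 3 is determined when the first two match (AABB, BBAA), so with probability 2/6 = 1/3. Place 4 is always determined. Expected number: 0 + 0 + 1/3 + 1 = 4/3 of 4, or 33.3%.

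3. **By site.**
   - Srinagarind, 100 patients: 25 blocks × 4/3 = 33.3.
   - Each site of 50: 12 full blocks × 4/3 = 16.0. The two remaining places are the first two of a block and add nothing.
   - Total: 33.3 + 16.0 + 16.0 = 65.3 of 200, or 32.7%.

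4. **Best guess.** Someone who always names the arm with more places left in the block is right with probability 1/2, 2/3, 2/3 and 1 at the four places (place 3: 1/3 × 1 + 2/3 × 1/2 = 2/3). The sum is 17/6 of 4, or 70.8%. At a site of 50: (12 × 17/6 + 1/2 + 2/3)/50 = 70.3%. Over the 200: 70.6%. Simple randomisation would give 50%.

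5. **Alternatives.** Fixed sizes are enumerated exactly over full blocks. Varying sizes were simulated at a site of 50, with sizes equally likely and a guesser who knows which sizes are in use.

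| Scheme | Known with certainty | Best guess right |
|---|---|---|
| Fixed 4 | 33.3% | 70.8% |
| Fixed 6 | 25.0% | 68.3% |
| Fixed 8 | 20.0% | 66.6% |
| Random 4, 6 | 5.7% | 69.0% |
| Random 4, 6, 8 | 2.4% | 67.7% |

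For random 4, 6 and 8, 2.4% of 200 is about 5 patients. A simulation at a site of 100 gave a best-guess rate of 68.0%.

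6. **How much guessing the change removes.** Measure the excess over chance as 2p − 1. At a site of 50 it goes from 2 × 0.703 − 1 = 0.406 to 2 × 0.677 − 1 = 0.354, a fall of about 13%. Varying the sizes removes nearly all of the certainty but little of the general guessability.

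7. **Exact balance under the present scheme.** Since 50 is not a multiple of 4, a 25/25 split at a site of 50 needs the last two places to differ, with probability 4/6. At both such sites the probability is (4/6)² = 44%.

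**The case against.** The strongest reply is that the one third counts predictable places and does not measure bias. It requires that patients are randomised one at a time, that recruiting staff know the order of earlier allocations at their site, and that they know the block size. Only the last is in the documents directly. Recruitment spread over clinic visits makes one-at-a-time allocation likely, but randomising all patients together after enrolment is not excluded and would remove the problem. This stands, and it makes the figure a ceiling.

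The room to steer is also limited. Srinagarind had 91 PD patients in 2016 and is to enrol 100, so unless the clinic has grown well beyond that, few can be turned away. With visits within two months and recruitment over three, a deferred patient has roughly one further scheduled visit. This too stands, although reordering remains possible.

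A reader might infer that selection bias would go unnoticed. The documents do not support that. Prognostic covariates are collected at enrolment, including previous OH admissions, co-morbidities and months on PD. Baseline is described by arm, important imbalances are adjusted for, and patients who decline or are excluded are listed, though the text names only one hospital. These checks are partial but real. The fact that nephrologists who can see the arm decide on interventions is a separate ascertainment problem, and blinding them would not expose selection.

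A reader might also infer that the recruiter judges app use. The inclusion criterion names no assessor.

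Finally, varying the block sizes barely changes the best-guess rate. That is correct, and it is why the missing release procedure has to be dealt with at the same time.

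**Conclusion.** The point holds as a conditional one. With fixed blocks of four at each site, up to 65 of 200 allocations (32.7%) could be known before the patient is enrolled. The conditions are that allocation is sequential and that staff keep track of earlier assignments. That the trial is open is inferred from the visibly different arms and the absence of any described blinding; the protocol does not use the term.

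It would be tempting to say that recruiters will know a third of allocations, or that the rate difference will be biased by some amount. Neither follows. Nothing in the documents shows what recruiting staff will track or do, and no effect on the assumed rates of 2.3 and 4.6 per patient-year can be derived from the block size.

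The change should be made because the weakness is avoidable at little cost and because the existing checks would reveal or correct steering only in part. It does not invalidate the design.

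**What to change.** Amend Aim 2, Randomization, in four respects:

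- Generate the three site lists away from recruiting staff, for example at the university data management centre that already supports the project, with block sizes drawn at random from 4, 6 and 8.
- Keep the block sizes out of site-facing documents.
- Release each allocation singly, and only after consent and every eligibility check, including the app-use demonstration, have been recorded.
- State that patients are randomised one at a time. If they are instead to be randomised together after enrolment, say that, and the concern falls away.

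The cost is a small change to the randomisation program, a short protocol edit and a simple controlled-release step at three sites. Arm totals at a site may differ by a few patients. The present scheme does not guarantee the planned 25/25 split at the two smaller sites either, so little is given up.
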